## **5.6 Definition of Baseline**

For all analyses, the baseline value for each measure is defined as the last non-missing value prior to IP administration. Note that, for some participants for whom randomization system errors delayed randomization by one calendar day, procedures performed the day before Day 1 were considered acceptable without being repeated on the actual Day 1.

## **5.7 Multiple Records in an Analysis Window**

If more than one sample is collected for anti-CHIKV human SNA assay assessment for a given time point, the sample closest to the nominal time point is used for analysis tabulations. If there is a tie (i.e., the two samples are an equidistant number of days from the nominal time point), then the geometric mean of the two titers is used for analysis tabulations. All samples are reported with database visit and analysis visit in data listings by participant.

## **5.8 Coding Dictionaries**

Medical history and AEs are coded to system organ class (SOC) and preferred term (PT) based on the Medical Dictionary for Regulatory Activities (MedDRA) dictionary version 24.1.

Prior and concomitant medications and vaccines are coded according to the World Health Organization's (WHO) WHODrug Global Dictionary version C32021 to Anatomical Therapeutic Chemical (ATC) classification and preferred drug name.

## **5.9 Adverse Event Toxicity/Severity Grading**

With the exception of redness and swelling, all solicited AEs are graded by the investigator according to severity grading scales from “mild” to “potentially life-threatening.” The severity of redness and swelling, recorded as a diameter (mm) in the solicited adverse event diary, are summarized according to categories based on the largest-diameter linear measurement when a local reaction is present:

- Grade 0/absent = 0-24 mm.
- Grade 1/mild = 25-50 mm.
- Grade 2/moderate = 51-100 mm.
- Grade 3/severe = >100 mm.
- Grade 4/potentially life threatening = necrosis or exfoliative dermatitis.

Events reported as not present (0 mm is entered) are reported as Grade 0. Similarly, body temperatures recorded by the participant that are below 100.4° result in fever reported as Grade 0/absent.

Solicited AEs other than redness and swelling and unsolicited AEs are graded by the investigator for severity. The severity grading scales (Grade 1 = mild, Grade 2 = moderate, Grade 3 = severe, Grade 4 = potentially life-threatening) that are used for safety assessment in this study are provided in Appendix I of this document and the protocol, based on the *FDA*

*Guidance for Industry: Toxicity Grading Scale for Healthy Adult and Adolescent Volunteers Enrolled in Preventative Vaccine Clinical Trials* (2). Note that AEs that result in death are classified as Grade 4 and indicated as resulting in death.

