8.1.8 Severity of Adverse Events

The investigator will grade all AEs for severity. For the study Grading Scale see [Appendix I](#). Adverse events not listed in the Grading Scale will be graded as follows:

- **Mild** (Grade 1) – No interference with activity
- **Moderate** (Grade 2) – Some interference with activity
- **Severe** (Grade 3) – Significant; prevents daily activity
- **Potentially Life-Threatening** (Grade 4) – as determined at ER visit or hospitalization
- For solicited AEs, the severity of redness and swelling recorded as diameters (mm) will be summarized according to categories based on the largest diameter linear measurement when the local reaction is present.
- Events reported as not present (0 mm is entered) will be reported as Grade 0.

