15 APPENDICES

APPENDIX I TOXICITY GRADING SCALE TABLES

Local Reaction to Injectable Product	Mild (Grade 1)	Moderate (Grade 2)	Severe (Grade 3)	Potentially Life Threatening (Grade 4)
Pain	Does not interfere with activity	Repeated use of non-narcotic pain reliever >24 hours or interferes with activity	Any use of narcotic pain reliever or prevents daily activity	Emergency room (ER) visit or hospitalization
Tenderness	Mild discomfort to touch	Discomfort with movement	Significant discomfort at rest	ER visit or hospitalization
Erythema/Redness*	25 – 50 mm***	51 – 100 mm***	>100 mm***	Necrosis or exfoliative dermatitis
Induration/Swelling**	25 – 50 mm*** and does not interfere with activity	51 – 100 mm*** or interferes with activity	>100 mm*** or prevents daily activity	Necrosis

*In addition to grading the measured local reaction at the greatest single diameter, the measurement should be recorded as a continuous variable.

**Induration/Swelling should be evaluated and graded using the functional scale as well as the actual measurement.

***Revised by sponsor.

Vital Signs*	Mild (Grade 1)	Moderate (Grade 2)	Severe (Grade 3)	Potentially Life Threatening (Grade 4)
Fever (°C)** (°F)**	38.0 – 38.4 100.4 – 101.1	38.5 – 38.9 101.2 – 102.0	39.0 – 40 102.1 – 104	>40 >104
Tachycardia – beats per minute	101 – 115	116 – 130	>130	ER visit or hospitalization for arrhythmia
Bradycardia – beats per minute***	50 – 54	45 – 49	<45	ER visit or hospitalization for arrhythmia
Hypertension (systolic) – mmHg	141 – 150	151 – 155	>155	ER visit or hospitalization for malignant hypertension
Hypertension (diastolic) – mmHg	91 – 95	96 – 100	>100	ER visit or hospitalization for malignant hypertension

Vital Signs*	Mild (Grade 1)	Moderate (Grade 2)	Severe (Grade 3)	Potentially Life Threatening (Grade 4)
Hypotension (systolic) – mmHg	85 – 89	80 – 84	<80	ER visit or hospitalization for hypotensive shock
Respiratory Rate – breaths per minute	17 – 20	21 – 25	>25	Intubation

*Participant should be at rest for all vital sign measurements.

**Oral temperature; no recent hot or cold beverages or smoking.

***When resting heart rate is between 60 – 100 beats per minute. Use clinical judgement when characterizing bradycardia among some healthy participant populations, for example, conditioned athletes.

Systemic (General)	Mild (Grade 1)	Moderate (Grade 2)	Severe (Grade 3)	Potentially Life Threatening (Grade 4)

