**APPENDIX II TOXICITY GRADING SCALE**

EVENT	MILD (Grade 1)	MODERATE (Grade 2)	SEVERE (Grade 3)	POTENTIALLY LIFE THREATENING (Grade 4)
Fever	≥100.4-101.1°F (≥38.0-38.4°C)	≥101.2-102°F (≥38.5-39°C)	≥102.1°F-104°F (≥39°C-40°C)	>104°F 
Headache	No interference with activity	Some interference with activity, may require repeated use of non-narcotic pain reliever for more than 24 hours	Significant, prevents daily activity, any use of narcotic pain reliever	ER visit or hospitalization
Fatigue	No interference with activity	Some interference with activity	Significant, prevents daily activity	ER visit or hospitalization
Myalgia	No interference with activity	Some interference with activity	Significant, prevents daily activity	ER visit or hospitalization
Nausea	No interference with activity	Some interference with activity	Significant, prevents daily activity	ER visit or hospitalization for hypotensive shock
Vomiting	1-2 episodes/24 hours	>2 episodes/24 hours	Requires IV hydration	ER visit or hospitalization for hypotensive shock
Diarrhea	2-3 loose stools or <400 g/24 hours	4-5 stools or 400-800 g/24 hours	6 or more watery stools or >800 g/24 hours or requires outpatient IV hydration	ER visit or hospitalization
Injection site pain	Does not interfere with activity	Repeated use of non-narcotic pain reliever > 24 hours or interferes with activity	Use of any narcotic pain reliever or prevents daily activity	ER visit or hospitalization
Injection site erythema/redness	25-50 mm	51 mm-100 mm	>100 mm	Necrosis or exfoliative dermatitis
Injection site induration/swelling	25-50 mm and does not interfere with activity	51 mm-100 mm or interferes with activity	>100 mm or prevents daily activity	Necrosis

Document Approvals  
Approved Date: 03 Apr 2023

Document Approval Task Verdict: Approve	Sr Director, Biostatistics & Data Sciences [REDACTED]
Document Approval Task Verdict: Approve	Sr. Manager, Clinical Trials [REDACTED]
Document Approval Task Verdict: Approve	Director, Biostatistics [REDACTED]
Document Approval Task Verdict: Approve	VP, Clinical Development [REDACTED]

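### Injection-site swelling is tabulated by diameter alone for Grades 0–3, although both grading appendices also grade it by its effect on activity, so activity-limiting swelling can be under-graded

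*SAP*

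**What the plan says.** The body text of both documents uses a diameter rule. Protocol 8.1.8 says that redness and swelling, recorded in millimetres, "will be summarized according to categories based on the largest diameter linear measurement when the local reaction is present". SAP 5.9 repeats this: they "are summarized according to categories based on the largest-diameter linear measurement when a local reaction is present". It then lists the bands, among them "Grade 0/absent = 0-24 mm", "Grade 1/mild = 25-50 mm" and "Grade 3/severe = >100 mm", with 51–100 mm as Grade 2. No functional condition is attached. Only Grade 4 (necrosis or exfoliative dermatitis) does not depend on diameter. SAP 5.9 also takes the two signs out of investigator grading: "With the exception of redness and swelling, all solicited AEs are graded by the investigator according to severity grading scales".

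The appendices use a combined rule for swelling. In Protocol Appendix I and SAP Appendix II, Grade 1 needs 25–50 mm and no interference with activity. Grade 2 is 51–100 mm or interference with activity. Grade 3 in the SAP reads ">100 mm or prevents daily activity", and the protocol row is equivalent. Grade 4 is necrosis. The protocol adds a footnote: "Induration/Swelling should be evaluated and graded using the functional scale as well as the actual measurement". The redness row has no functional criterion in either appendix.

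SAP 9.2 refers severity coding to Section 5.9 and Appendix II together. Protocol 3.2.9 and SAP 9.2.2 have the investigator assess the severity of solicited AEs and make no exception for swelling.

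**The concern.** The documents give two different rules for the same solicited event and no order of precedence. A programmer cannot apply both wherever swelling limits activity at a modest diameter.

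Safety is one of the coprimary objectives, and solicited AEs through Day 8 are a listed safety endpoint. The outputs that depend on the swelling grade include SAP Tables 14.3.2.2.1 to 14.3.2.2.4 (highest severity), 14.3.2.3 (Grade 3 or higher) and 14.3.2.4 (treatment-related). Below 25 mm the consequence goes beyond a lower grade: swelling that limits activity would be labelled absent and would not count as swelling.

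**Working it through.** The plan states no figure on this point, so there is none to reproduce. The check applies the two rules to the same event and compares the grades.

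**Inputs.** The SAP 5.9 bands are 0–24, 25–50, 51–100 and >100 mm for Grades 0, 1, 2 and 3. The appendix swelling row is the one described above. The word *or* in that row is read literally, so the functional condition alone is sufficient at any diameter. For the first line of the table, some swelling is present but measures under 25 mm.

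**Rules.**
- SAP 5.9: the grade depends on diameter only.
- Appendices: Grade 3 if the diameter exceeds 100 mm or daily activity is prevented. Otherwise Grade 2 if it exceeds 50 mm or activity is interfered with. Otherwise Grade 1 from 25 mm, and Grade 0 below that.

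| Largest diameter | SAP 5.9 | Appendix: no interference | Appendix: interferes | Appendix: prevents daily activity |
|---|---|---|---|---|
| under 25 mm | 0 | 0 | 2 | 3 |
| 25–50 mm | 1 | 1 | 2 | 3 |
| 51–100 mm | 2 | 2 | 2 | 3 |
| over 100 mm | 3 | 3 | 3 | 3 |

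**Result.** The rules disagree in 5 of the 12 combinations, and SAP 5.9 gives the lower grade each time.
- Swelling that prevents daily activity: 3 − 0 = 3 grades lower under 25 mm, 3 − 1 = 2 lower at 25–50 mm, and 3 − 2 = 1 lower at 51–100 mm.
- Swelling that interferes with activity: 2 − 0 = 2 grades lower under 25 mm, and 2 − 1 = 1 lower at 25–50 mm.
- Without interference, the rules agree at every diameter.

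**Scale.** Protocol 1.8.1 reports no injection-site swelling among the 50 participants in the earlier phase 2 group that received this regimen. The exact two-sided 95% upper bound for 0 of 50 is 1 − 0.025^(1/50) = 0.071, or 7.1%. Applied to 200 vaccinees this is 200 × 0.071 ≈ 14 people with any swelling, of whom only some would have activity-limiting swelling. That study enrolled adults aged 18 to <46 (Protocol 1.4.3), so carrying the bound over to age 65 and above is an assumption.

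**The case against.** The strongest reply is that SAP 5.9 follows the protocol body almost exactly, so diameter grading is an explicit, prespecified convention. It is true that the SAP does not depart from Protocol 8.1.8. But the protocol's own footnote requires both scales, so the conflict is between body text and appendix in both documents.

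The second reply is that little is lost. Safety endpoints are reported for information only. SAP 9.2.2 also records swelling as an unsolicited AE if it is serious, medically attended or ongoing after Day 8. Injection-site pain keeps its functional grading, so a participant whose disabling swelling is also painful may still appear as having a Grade 3 solicited event. All this limits the effect, although the overlap with pain is an inference. None of it corrects the swelling rows.

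The third reply is that a functional grade may not exist. The diary text in Protocol 3.2.9 asks for a diameter, and SAP 5.9 excludes swelling from investigator grading. Against that, Protocol 3.2.9 has the investigator assess the severity of all solicited AEs and enter the result on the solicited AE eCRF. The documents do not settle what was captured, so this objection stands as a condition on the remedy.

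A reader might also draw three stronger conclusions that the documents do not support:
- **That SAP 5.9 can only lower swelling grades.** This holds for Grades 0–3. At Grade 4, 5.9 adds exfoliative dermatitis, which the appendices list for redness but not for swelling, so there it is the broader rule.
- **That calling 0–24 mm absent is a separate error.** Both appendices start at 25 mm when activity is unaffected. The label conflicts with them only for small swelling that limits activity.
- **That any swelling with a functional score of 1 should count as present.** The mildest functional level means no interference. A harmless 5 mm swelling would then become Grade 1, although both appendices also require 25–50 mm for that grade.

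**Conclusion.** The inconsistency is real, and nothing in either document resolves it. For Grades 0–3, following SAP 5.9 under-grades swelling of 100 mm or less that prevents daily activity by one to three grades. It under-grades swelling of 50 mm or less that interferes with activity by one or two.

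The number of affected events is unknown and probably small. Immunogenicity endpoints, power and alpha are untouched. A reader might infer that the solicited tables will conceal a material number of severe reactions, or will bias the comparison with placebo. The documents give no event counts to support either.

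The conclusion rests on the literal reading of *or* in the appendix rows. Whether the grades can be corrected, or only qualified, depends on whether a functional assessment of swelling was recorded.

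**What to change.** Before unblinding, reconcile Protocol 8.1.8, SAP 5.9 and SAP 9.2.2 with the two appendices by tabulating swelling on the appendix row:
- Start from the diameter grade. Raise it to Grade 2 if the investigator records interference with activity, and to Grade 3 if daily activity is prevented. Never lower it.
- Keep swelling under 25 mm without interference at Grade 0.
- Keep redness on diameter for Grades 0–3.
- Use necrosis as Grade 4 for swelling, as in the appendices.
- Correct the reference in SAP 5.9 to Appendix I of the SAP; the scale is in SAP Appendix II.

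First confirm that the solicited AE eCRF holds the investigator's functional assessment of swelling. If it does not, state in the SAP and the report that swelling grades are diameter-only and may understate severity relative to the adopted scale.

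If the assessment was captured, the cost is revised wording and one derivation rule; if not, it is a stated limitation. The downside for the sponsor is that swelling grades may look slightly less favourable.

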## 6 STATISTICAL CONSIDERATIONS

### 6.1 Statistical Considerations

Data summaries are tabulated by appropriate grouping for each analysis population as specified in Section 5.4.

Continuous endpoints are summarized by descriptive statistics including number of non-missing observations (n), mean, SD, median, minimum, and maximum. In the analysis of the anti-CHIKV SNA data as a continuous variable, anti-CHIKV SNA values are logarithmically transformed (base10), and the GMTs and associated 95% CI for each treatment group are computed by exponentiating the corresponding log-transformed means and two-sided 95% CIs. Categorical variables are summarized by frequency counts (n) and percentages of participants (%) in each category, including missing or unknown when appropriate.

Unless otherwise specified, CIs and hypothesis tests are two-sided with 95% confidence (or one-sided with 97.5% confidence).

The reporting conventions to be applied to all tables, listings and figures are included in a living document that accompanies the table and listing shells. All derivations, statistical analyses, summaries, and listings are generated using SAS Version 9.4 or higher (SAS Institute, Inc., Cary, North Carolina, United States).

#### 6.1.1 Seroresponse Rates

The superiority of the immune response to PXVX0317 vaccine over that to placebo is demonstrated at Day 22 by comparing seroresponse rates between the two treatment groups (the percentage of participants with an anti-CHIKV human SNA assay titer █, considered the presumptive seroprotection rate). Percentages of participants with anti-CHIKV SNA █ seroresponse rate and secondary response rates at  $\geq 15$  and 4-fold rise over baseline are reported with associated two-sided 95% Wilson score method CIs (keyword /BINOMIAL (WILSON) on tables statement). The difference in seroresponse rates between the PXVX0317 and placebo groups is calculated, along with the 95% CI for the difference based on the Newcombe hybrid score method (keyword /RISKDIFF (CL=NEWCOMBE)). The lower bound of the two-sided 95% CI on the difference in seroresponse rates between PXVX0317 and placebo must be █. Additionally, the null hypothesis of no difference between seroresponse rate percentages is tested using a two-sided chi-square test with alpha=0.05. No multiplicity adjustment is employed, and no covariate adjustment is performed. See Section 6.4 for statistical hypothesis, Section 6.9 for multiplicity considerations, and Section 8.4.1.1 for analysis outputs

Identical methods will be used for treatment group comparison of seroresponse rates at Days 15 and 183.

### 6.1.2 Geometric Mean Titers and Geometric Mean Fold Increase

The superiority of PXVX0317 vaccine immunogenicity over that of placebo is explored further by comparing Day 22 GMTs derived from a linear model with a one-sided alpha=0.025. The primary model is an analysis of variance (ANOVA), with  $\log_{10}$ -transformed anti-CHIKV SNA titers ( $\log_{10}$ ) as the dependent variable and treatment group and study site as the fixed effects in the model. No interaction term is used. The adjusted least square means and their 95% CIs calculated based on the ANOVA are back transformed and reported as the group GMT values. No adjustment for multiplicity is applied. See Section 6.4 for statistical hypothesis, Section 6.9 for multiplicity considerations, and Section 8.4.1.2 for analysis outputs. Identical methods are used for treatment group comparison of GMTs at Days 15 and 183.

Geometric mean fold increase (GMFI) from baseline (Day 1) to Days 15, 22 and 183 is calculated using the difference from Day 1 in  $\log_{10}$ -transformed titers as the dependent variable in the ANOVA model. The adjusted least square means and their 95% CIs calculated based on the ANOVA are back transformed and reported as the group GMFI values. The median, minimum and maximum titers and fold-increases are based on the non-transformed scale.

